## 7.5.2 Secondary Efficacy Analyses

### 7.5.2.1 Percent change from baseline in AN count at Week 16

This secondary endpoint will be analyzed using a similar MMRM model as for the primary endpoint. The percent change from baseline in AN count at Week 16 will be the response variable.

### 7.5.2.2 Proportion of subjects achieving HiSCR50 at Week 16

The frequency and percentage of subjects with HiSCR50 will be summarized at Week 16. The unadjusted risk difference and 90% exact unconditional confidence intervals will be reported between the imidolimab and placebo groups for all subjects and Hurley Stage at randomization (Stage II or III). The common risk difference will also be tested using a generalized Cochran-Mantel-Haenszel test (ANOVA for row means), adjusting for Hurley Stage at randomization.

A sensitivity analysis will be conducted for this endpoint on the ITT Analysis Set where subjects received rescue medications between Week 4 and Week 16 will be considered as failure to achieve HiSCR50 at Week 16.

An additional exploratory analysis will be performed for the proportion of subjects achieving HiSCR50 by visit. A repeated-measures generalized estimating equations (GEE) with the logit link will be used. The model will include treatment, visit, treatment by visit interaction, race, gender, Fitzpatrick skin type, Hurley Stage at baseline, and baseline inflammatory lesion count as covariates. Data from protocol specified visits up to Week 16 will be included in the analysis. An unstructured correlation matrix will be used to model correlation within a patient; if convergence is an issue, a Toeplitz structure may be considered. An odds ratio resulting from this model along with 90% CI will be reported.

### 7.5.2.3 Change from Baseline in Average HS pain NRS at Week 16

Change from baseline in Average HS pain NRS at Week 16 will be analyzed using a similar MMRM model as for the primary endpoint, but changing baseline AN count to HS pain NRS in the model as the response.

### 7.5.2.4 Percent change from Baseline in Average HS pain NRS at Week 16

Percent change from baseline in Average HS pain NRS at Week 16 will be analyzed similarly to percent change from baseline in AN count at Week 16, as described in **Section 7.5.2.1**.

### 7.5.2.5 Change from Baseline in Worst HS pain NRS at Week 16

Change from baseline in Worst HS pain NRS at Week 16 will be analyzed using a similar MMRM model as for the primary endpoint, but changing baseline AN count to HS pain NRS in the model as the response.

### 7.5.2.6 Percent change from Baseline in Worst HS pain NRS at Week 16

Percent change from baseline in Worst HS pain NRS at Week 16 will be analyzed similarly to percent change from baseline in AN count at Week 16, as described in **Section 7.5.2.1**.

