#### 9.4.6.1 CATEGORICAL ENDPOINTS

Frequency and percentages for each response Yes/No for categorical endpoints will be presented separately by visit for each treatment arm. Subjects with missing scores at a given visit will be considered to have not met the criteria of interest (ie, nonresponse). Estimates of the difference between treatments (imsidolimab – placebo) will be presented along with exact 90% CIs. Treatment arms will be compared using Cochran–Mantel–Haenszel chi-squared test, adjusted for stratification factor (Hurley Stage at baseline (Stage II or III)).

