## 3. STUDY DESIGN

### 3.1 Study Design

This study is a Phase 2, multicenter, randomized, double-blind, placebo-controlled study to evaluate the efficacy and safety of imsidolimab in adult subjects with hidradenitis suppurativa (HS). This study will also characterize the pharmacokinetic (PK) profile of imsidolimab and explore the immune response to imsidolimab in subjects with HS.

To be eligible for this study, subjects must have a clinically confirmed diagnosis of HS with a disease duration of at least 6 months before Day 1. In addition, subjects will have the following characteristics at Screening and Day 1:

- 1) HS lesions present in at least 2 distinct anatomical areas, 1 of which must be Hurley Stage II (i.e., single or multiple, widely separated, recurrent abscesses with tract formation and cicatrization) or Hurley Stage III (i.e., diffuse or near diffuse involvement, or multiple interconnected tracts and abscesses across the entire area);
- 2) total abscess and inflammatory nodule (AN) count of  $\geq 5$ ;
- 3)  $\leq 20$  draining fistulas.

Randomization will be stratified based on Hurley Stage at baseline (Stage II or III).

The maximum study duration per subject is approximately 44 weeks, which includes a screening period of up to 30 days, followed by a 16-week placebo-controlled period, a 16-week treatment extension period, and an 8-week follow up period. The placebo-controlled period ends at Day 113 (Week 16) and the treatment extension period starts when study treatment is administered at the Week 16 visit. Of note, during the extension period all subjects will receive imsidolimab but their treatment will remain blinded.

During the placebo-controlled period, eligible subjects will be randomized (1:1:1) to receive either imsidolimab (at 1 of 2 different regimens) or placebo, subcutaneously (SC) administered on 4 occasions: Day 1, Day 29 (Week 4), Day 57 (Week 8), and Day 85 (Week 12).

The treatment arms during the placebo-controlled period will be as follows:

[figure not shown]
- Imsidolimab 400 mg on Day 1, followed by 200 mg on Days 29, 57, and 85
- Imsidolimab 200 mg on Day 1, followed by 100 mg on Days 29, 57, and 85
- Placebo on Days 1, 29, 57, and 85

During the extension period, all subjects will receive imsidolimab, SC administered on 4 occasions:

- 400 mg dose of imsidolimab on Day 113 for subjects assigned to placebo arm 3A during the placebo-controlled period, followed by 200 mg doses on Days 141, 169, and 197

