### 7.5 Efficacy Analyses

The ITT Analysis Set will be used as the primary analysis set for all efficacy analyses in the placebo-controlled period. The Extension Analysis Set will be used as the main analysis set for all efficacy analyses in the extension period.

Per protocol analyses will be performed on the primary as well as the following secondary endpoints:

- Percent change from baseline in AN count at each visit
- Proportion of subjects achieving HiSCR50 at each visit
- Change from baseline in HS Pain NRS at each visit
- Percent change from baseline in HS Pain NRS at each visit

All statistical tests will be performed at the 10% level of significance unless otherwise stated. All confidence intervals will be reported as 2-sided 90% confidence intervals unless otherwise stated. Descriptive statistics will be provided for the continuous variables as number of subjects, mean, standard deviation, standard error of the mean, first and third quartiles, minimum, and maximum. Descriptive summaries of continuous variables will be shown for baseline, change from baseline to endpoint, and percent change from baseline to endpoint. All data will be listed in data listings.

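### The HiSCR50 estimate and its exact 90% interval ignore Hurley stage while the test is stratified by it, and the common risk difference being tested is never estimated

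*SAP*

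**What the plan says.** SAP 7.5.2.2 gives the effect measure and interval for HiSCR50 at Week 16: "The unadjusted risk difference and 90% exact unconditional confidence intervals will be reported between the imidolimab and placebo groups". They are given for all subjects and again within each Hurley stage. The next sentence gives the test: "The common risk difference will also be tested using a generalized Cochran-Mantel-Haenszel test (ANOVA for row means), adjusting for Hurley Stage at randomization".

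Protocol 9.4.6.1 pairs the same two elements for every categorical endpoint. The interval is described as follows: "Estimates of the difference between treatments (imsidolimab – placebo) will be presented along with exact 90% CIs". The comparison is a CMH test adjusted for Hurley stage.

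The levels of test and interval are meant to correspond (SAP 7.5): "All statistical tests will be performed at the 10% level of significance unless otherwise stated" and "All confidence intervals will be reported as 2-sided 90% confidence intervals unless otherwise stated".

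Randomization is stratified by Hurley stage (SAP 3.1 and 3.2). For the primary endpoint, SAP 7.5.1 takes the estimate, interval and test from one model that includes Hurley stage.

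SAP Appendix 2 has a template labelled as the exact unconditional CI. It requests `EXACT OR` on an unstratified treatment-by-outcome table.

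**The concern.** The test asks whether the arms differ once Hurley stage is allowed for. The overall estimate and interval leave Hurley stage out. The SAP names a common risk difference as the thing tested but gives it no estimate and no interval. The by-stage differences do not fill the gap, because no rule combines them.

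Readers expect a 90% interval and a test at the 10% level to agree about zero. Here they need not. A CMH p-value below 0.10 can stand beside an interval that includes zero, which leaves two answers for the responder endpoint. Under SAP 3.4 the Week 16 secondary results go to the sponsor's executive management for development decisions, so the estimate and interval will be read directly.

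**Working it through.** **Inputs from the documents.** 40 per arm, 36 after 10% dropout (40 × 0.9 = 36; SAP 3.5); test level 0.10 and 90% intervals (SAP 7.5). Both arm sizes matter. SAP 6.2.3 counts only subjects with HiSCR50 data, and Protocol 9.4.6.1 counts missing as nonresponse.

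**Plan's own figure.** None exists for HiSCR50 beyond the nominal 90%. The arm size does reproduce: 36 per arm, a difference of 4.9 and SD 8.2 give 80.7% power for the primary endpoint (noncentral t), against the stated 80%.

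**Assumptions.** Control rates, Hurley split and true differences are assumed. The SAP does not name the statistic that orders tables in the exact method, so two were run: the raw difference and the score statistic.

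**Cause 1: the exact construction, with no Hurley effect.** The interval inverts two one-sided 0.05 tests, each maximized over the unknown common rate. Full enumeration with true differences of 0 to 30 points gives this coverage of the nominal 90% interval:

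| Ordering | Control rates | 40 per arm | 36 per arm |
|---|---|---|---|
| Score | 10-60% | 90.3-92.2% | 90.4-92.4% |
| Raw difference | 20-40% | 91.0-96.5% | 91.6-97.3% |
| Raw difference | 10-60% | 90.7-99.5% | 91.6-99.6% |

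**Cause 2: ignoring the strata.** With strata balanced between arms, the unadjusted difference varies only by the within-stage variance, but its interval is built on the pooled variance. Take an assumed 24/16 split (60% Stage II).

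- Control rates 40%/20%: pooled rate 0.6 × 0.4 + 0.4 × 0.2 = 0.32. Pooled variance 0.32 × 0.68 = 0.2176. Within-stage variance 0.6 × 0.24 + 0.4 × 0.16 = 0.2080. SE ratio √(0.2176/0.2080) = 1.023.
- Control rates 50%/10%: pooled rate 0.34. Pooled variance 0.34 × 0.66 = 0.2244. Within-stage variance 0.6 × 0.25 + 0.4 × 0.09 = 0.1860. SE ratio √(0.2244/0.1860) = 1.098.

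In large samples an interval of ±1.645 SE widened by these ratios covers 2Φ(1.645 × 1.023) − 1 = 90.8% and 2Φ(1.645 × 1.098) − 1 = 92.9%. If Hurley stage is not prognostic the ratio is 1 and this cause disappears.

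**Both causes together.** Enumeration with these prognostic strata gives coverage of 91.6-94.2% (score) and 92.4-96.0% (raw).

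**Disagreement with the test.** The share of all trials with CMH p < 0.10 and an exact 90% interval that includes zero, at 24/16 in each arm, is:

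| Control II/III | Active II/III | Raw | Score |
|---|---|---|---|
| 30%/30% | 30%/30% | 3.5% | 1.3% |
| 40%/20% | 40%/20% | 3.7% | 2.2% |
| 40%/20% | 60%/40% | 2.4% | 2.3% |
| 50%/10% | 70%/30% | 8.4% | 8.4% |

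Across all balanced layouts (24/16, 20/20 and 22/14) with a true benefit of 15 to 20 points, the range is 1.2-11.8% (raw) and 0.9-11.2% (score). The reverse, p ≥ 0.10 with zero excluded, did not occur. With strata unbalanced between arms, disagreement ran from under 0.1% to 26%, and the reverse reached at most 1.5%.

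A further case has 22/18 per arm, control rates 45%/15% and a 20-point benefit. CMH is significant in 61% of trials, and the exact interval excludes zero in 55% under either ordering.

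**One table.** 15/40 against 8/40, treated as one stratum. Expected active responders are 23/2 = 11.5. Variance = 40 × 40 × 23 × 57/(80² × 79) = 4.149. Chi-square = (15 − 11.5)²/4.149 = 2.953, p = 0.086. The raw-ordered exact 90% interval is about −0.02 to 0.36. The score-ordered one is about 0.005 to 0.335. Whether zero is included depends on a choice the SAP does not state.

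**The alternative.** In stratum h, let n₁ and n₀ be the arm sizes, N = n₁ + n₀, m the total responders and d the risk difference. The weight is w = n₁n₀/N. At a difference of zero the score variance of d is (m/N)(1 − m/N)(1/n₁ + 1/n₀) × N/(N − 1). Then Σwd is the observed minus expected active responders, and Σw²Var(d) = Σ n₁n₀m(N − m)/[N²(N − 1)]. These are the CMH numerator and variance, so the stratified score interval and the CMH test agree about zero by construction. Its coverage was 89.7-90.1% in the scenarios run. A Mantel-Haenszel difference with the Sato variance covered 88.3-89.3% and disagreed with CMH in 0.1-2.9% of trials.

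**The case against.** The strongest reply is that little depends on this. Protocol 9.1 and SAP 3.3 make all secondary comparisons exploratory. No success rule uses HiSCR50, and the exact interval did not cover less than 90% in any scenario run. That stands, and it limits the weight of the point.

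An unadjusted risk difference is also a legitimate marginal summary, and the SAP labels it openly. That stands too, but it does not supply an estimate of the common difference that the next sentence tests. SAP 7.5.2.2 does offer one Hurley-adjusted effect with an interval, an odds ratio from an exploratory GEE model by visit. That is on another scale and comes from a model with other covariates, so it does not fill the gap.

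Exact intervals are reasonable for the by-stage tables, which would hold about 16 to 24 subjects per arm under the assumed splits. That argues for keeping them there, not for the overall estimate.

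A reader might infer that the 90% interval really covers about 93-97%. The documents do not support that range. It needs raw-difference ordering and particular response rates, and the plan gives neither. A reader might also infer that the over-coverage is caused by the mismatch with the stratified test. Much of it under raw ordering exists with no Hurley effect at all; the strata add to it only if Hurley stage is prognostic, which the documents do not quantify. Finally, the reverse disagreement cannot be called impossible, since it appeared in up to 1.5% of trials when the strata were unbalanced.

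**Conclusion.** The point holds in this limited form. The HiSCR50 estimate and interval do not match the Hurley-stratified test, the common risk difference has no estimate, and the interval is conservative for two distinct reasons. Coverage is about 90-94% with score ordering and about 91-97% with raw-difference ordering. The latter assumes control rates of 20-40% when Hurley stage has no effect, and runs higher outside them. With a 15 to 20 point benefit and balanced strata, roughly 1-12% of trials would show p < 0.10 beside an interval that includes zero. All of these figures rest on assumed rates and splits at 36 to 40 per arm.

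The template code is a separate, plain mismatch: it requests an odds ratio where the text promises a risk-difference interval. Nothing here touches the primary analysis or makes the HiSCR50 interval anti-conservative. It should be settled before unblinding because the cost is small.

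**What to change.** - In SAP 7.5.2.2, make the Mantel-Haenszel-weighted common risk difference across Hurley stages the HiSCR50 estimate. Report it with a stratified score (Miettinen-Nurminen type) 90% interval beside the CMH p-value. State the weights and the N/(N − 1) variance factor, because that version matches CMH at zero, and use the same Hurley value as the test.
- Apply the same rule to the other responder endpoints under Protocol 9.4.6.1 and 9.4.7.
- Keep exact intervals for the within-stage and other sparse tables, and name the ordering statistic.
- Replace the `EXACT OR` template in SAP Appendix 2 with code for the risk-difference intervals that the text names.
- Record the change from the protocol's exact interval in SAP section 8.

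The cost is a few sentences and some template code, with no new data. The one downside is that the stratified interval is asymptotic. It covered 89.7-90.1% in the scenarios run, so it gives up the guarantee of at least 90% that the exact method provides.

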## 6.6 RESCUE TREATMENT

In the event that an intolerable painful lesion occurs that requires an immediate intervention, at Week 8 or later, physicians will have the option to perform protocol-allowed interventions. Only

two types of interventions are allowed: injection with intralesional triamcinolone acetonide suspension (at a concentration of up to 5 mg/mL, up to 1 cc) and incision and drainage. If incision and drainage is performed, the required over-the-counter antiseptic wash should continue to be used. New systemic and topical therapies following incision and drainage (including antibiotics) are prohibited. Concomitant use of wound care dressings is allowed; however, options are limited to alginates, hydrocolloids, and hydrogels. If a subject requires more than 2 lesion interventions during each of the double-blind phases of the study, they must be discontinued from the study.

All study visit evaluations must occur before any interventions are performed. Any lesion that undergoes an intervention will be documented in the source. The study site will be required to count any lesion that undergoes an intervention as permanently present from the date of the intervention and must account for it in the source and on the appropriate eCRF. All interventions (including local anesthetics) should be recorded in the eCRF for tracking purposes.

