#### 9.4.4 CONCOMITANT MEDICATION

All medications will be coded using the World Health Organization Drug Dictionary and Anatomical Therapeutic Chemical system. Each medication will be classified as prior medication if it is stopped prior to the first dose of study treatment, or as concomitant medication if it is ongoing at the time of the first dose or is started after the first dose of study treatment. Prior, concomitant, and rescue medications will be summarized descriptively with a by-subject listing.

To handle the issue of rescue medication use, the efficacy data on and after the use rescue medication will be set to missing in the efficacy analysis.

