#### 9.4.6 ANALYSIS OF THE SECONDARY EFFICACY ENDPOINTS

The ITT analysis set will be used for analysis of secondary efficacy endpoints. Following are the secondary efficacy endpoints:

- Percent change from Baseline in AN count at Week 16
- Proportion of subjects achieving HiSCR50 at Week 16

- Change from Baseline in HS Pain NRS at Week 16
- Percent change from Baseline in HS Pain NRS at Week 16

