### 6.2.3 Secondary Efficacy Variables

The secondary efficacy endpoints are as follows:

- **Percent change from baseline in AN count at Week 16**
- **Proportion of subjects achieving Hidradenitis Suppurativa Clinical Response 50 (HiSCR50) at Week 16**

The proportion of subjects with at least a 50% decrease from baseline AN count, and no increase in abscesses or draining fistulas in comparison to baseline (HiSCR50) at Week 16 will be calculated for each treatment group as follows:

A responder HiSCR50 is defined as a subject with

- a) at least a 50% decrease in AN count from Baseline, and
- b) no increase in abscess count relative to Baseline, and
- c) no increase in draining fistula count relative to Baseline

Having HiSCR50 data at Week 16 is defined as a subject who is either a responder HiSCR50 or can be confirmed to be a non-responder based on assessed data. Then, the proportion of subjects achieving HiSCR50 is defined as the following ratio:

$$\frac{\text{\# of subjects in treatment group achieving HiSCR50 responder status}}{\text{\# of subjects in treatment group having HiSCR50 data at Week 16}}$$

- **Change from baseline in worst HS Pain NRS scores at Week 16**
- **Percent change from baseline in worst HS Pain NRS scores at Week 16**
- **Change from baseline in average HS Pain NRS scores at Week 16**

- Percent change from baseline in average HS Pain NRS scores at Week 16

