# 7. STATISTICAL ANALYSIS

## 7.1 Data Handling Rules and Definitions, Including Handling of Missing Data

Except where specified, all continuous variables will be summarized with descriptive statistics (the number of non-missing values, mean, standard deviation, first and third quartiles, median, minimum, and maximum). Where data have been logarithmically transformed for analysis, the summary statistics on the back-transformed data will include the geometric mean (calculated as  $\exp(m)$ ), where  $m$  is the mean of the data on the log scale) and the coefficient of variation (calculated as  $100\sqrt{[\exp(s^2)-1]}$ , where  $s$  is the standard deviation of the data on the log scale). All categorical variables will be summarized with frequency counts and percentages. Tabulations will be provided based on all subjects combined, as well as separately by treatment group.

Missing data will be maintained as missing in the analysis datasets, unless specified otherwise. For variables where missing data are imputed, the analysis dataset will contain a new variable with the imputed value and the original variable value will be maintained as missing.

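### The protocol makes a rescued subject a HiSCR50 nonresponder in the main Week 16 analysis; the SAP does so only in a sensitivity analysis and does not declare the change

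*SAP*

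**What the plan says.** **Protocol.** Section 9.4.4 states that "the efficacy data on and after the use rescue medication will be set to missing in the efficacy analysis". The sentence covers efficacy analysis in general, not only the AN count. For categorical endpoints, Section 9.4.6.1 adds: "Subjects with missing scores at a given visit will be considered to have not met the criteria of interest (ie, nonresponse". Section 9.4.6 fixes the population: "The ITT analysis set will be used for analysis of secondary efficacy endpoints". Section 6.6 allows two kinds of rescue, an intralesional steroid injection and incision and drainage, and sets the earliest time: "at Week 8 or later, physicians will have the option to perform protocol-allowed interventions". It also has sites keep any treated lesion in the count permanently, and it discontinues a subject who needs more than two interventions in a double-blind phase.

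**SAP.** Section 6.2.3 defines HiSCR50 from lesion counts alone. The denominator is the number of "subjects in treatment group having HiSCR50 data at Week 16", and "Having HiSCR50 data at Week 16 is defined as a subject who is either a responder HiSCR50 or can be confirmed to be a non-responder" on assessed data. Rescue is not mentioned there. Section 7.1 sets the general rule: "Missing data will be maintained as missing in the analysis datasets, unless specified otherwise". No nonresponder rule is specified for HiSCR50. The rule that post-rescue data are missing appears only in component (c) of the AN-count estimand in Section 7.5.1. In Section 7.5.2.2 the main HiSCR50 analysis carries no rescue rule. A separate sensitivity analysis on the ITT set says that "subjects received rescue medications between Week 4 and Week 16 will be considered as failure to achieve HiSCR50 at Week 16". Section 6.1.3 records rescue medications and rescue procedures on two different CRF pages. Section 8, which lists changes from the protocol down to the spelling of questionnaire names, is silent on all of this.

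**The concern.** The protocol settles the status of a rescued subject in the main analysis, and the SAP moves that rule into a sensitivity analysis. The main Week 16 HiSCR50 rate can then be produced in more than one way from the same data, and the SAP does not say which way applies. HiSCR50 is the only responder endpoint among the secondary efficacy endpoints. Under SAP 3.4 the primary and secondary endpoints at Week 16 inform management's decisions on further development. An undeclared change in scoring leaves the reader unable to tell whether the reported rate follows the protocol.

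**Working it through.** **Plan's own figure.** The documents give no HiSCR50 rate, rescue rate or HiSCR50 power. Their only power statement concerns the AN count (difference 4.9, SD 8.2, 36 per arm, two-sided alpha 0.10, power 80%). It reproduces at 80.7% by the noncentral t distribution, but it says nothing about HiSCR50.

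**Step 1: the rules side by side, for a subject rescued before Week 16 who has Week 16 counts.**

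| Rule | Status in main analysis | In denominator? |
|---|---|---|
| Protocol 9.4.4 + 9.4.6.1 + 9.4.6 | Nonresponder | Yes (all ITT) |
| SAP, literal reading of 6.2.3 and 7.5.2.2 | Responder or nonresponder on counts | Yes |
| SAP, post-rescue data taken as missing | None | No |

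Neither SAP reading gives the protocol's result.

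**Step 2: can a rescued subject still respond on counts?** The minimum baseline AN count is 5. A 50% reduction requires AN ≤ 2.5, so 2 or less. Two treated lesions kept in the count give AN = 2 if all others clear, a 60% reduction. Response remains possible if abscess and draining fistula counts have not risen.

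**Step 3: effect on the difference.** Assume response *h* in unrescued subjects of 30% placebo and 50% active, rescue proportion *r*, and a proportion *q* of rescued subjects meeting HiSCR50 on counts. To isolate rescue, assume no dropout.

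- Protocol: rate = *h*(1 − *r*).
- SAP literal: rate = *h*(1 − *r*) + *qr*. The difference (active − placebo) changes by *q*(*r*_active − *r*_placebo).
- SAP with rescued subjects dropped: rate = *h*, so the difference is 50 − 30 = 20.0 points in every row.

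| *r* placebo / active | *q* | Protocol rates (difference) | SAP literal rates (difference) | SAP dropped (difference) |
|---|---|---|---|---|
| 10% / 5% | 0.3 | 27.0 / 47.5 (20.5) | 30.0 / 49.0 (19.0) | 20.0 |
| 15% / 10% | 0.3 | 25.5 / 45.0 (19.5) | 30.0 / 48.0 (18.0) | 20.0 |
| 20% / 10% | 0.4 | 24.0 / 45.0 (21.0) | 32.0 / 49.0 (17.0) | 20.0 |
| 15% / 15% | 0.3 | 25.5 / 42.5 (17.0) | 30.0 / 47.0 (17.0) | 20.0 |

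The literal reading shifts the difference by 0 to 4 points and raises the placebo rate by up to 8 points (24.0 to 32.0). The dropped reading shifts the difference by −0.5, +0.5, −1.0 and +3.0 points.

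Standard error of the difference with 40 per arm at 25.5% and 45.0%: √(0.255 × 0.745/40 + 0.45 × 0.55/40) = 0.105, or 10.5 points.

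**Step 4: one arm with dropout and the SAP denominator.** Take 40 randomised, 4 dropouts (the plan's 10%), 4 rescued with Week 16 counts, and 30% response among the other 32, so 9.6 responders.

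- Protocol: 9.6/40 = 24.0%.
- SAP literal, with 0, 1 or 2 of the 4 rescued qualifying: 9.6/36 = 26.7%, 10.6/36 = 29.4%, 11.6/36 = 32.2%.
- SAP with rescued dropped: 9.6/32 = 30.0%.
- SAP sensitivity rule with the same observed-case denominator: 9.6/36 = 26.7%.

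The last line shows that the sensitivity analysis does not recover the protocol's rate if it keeps the Section 6.2.3 denominator, because the 4 dropouts are still left out.

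**The case against.** The strongest reply is that the SAP is to be read together with the protocol (SAP Section 1), and Section 8 declares no departure from the set-to-missing rule. If that rule carries over, a rescued subject has no usable Week 16 HiSCR50 data and is never counted as a responder. The sensitivity analysis then makes sense, since it moves rescued subjects from excluded to failed. This is a fair reading, and it means that scoring rescued subjects as responders is not established. It does not remove the conflict: the protocol keeps those subjects in the denominator as nonresponders, and this reading removes them.

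The reply is also right that the effect is limited. A reader might infer that a response produced by the steroid injection is credited to the randomised arm. Protocol 6.6 largely blocks that, because the treated lesion stays in the count and only two interventions are allowed before discontinuation. A rescued subject can qualify only through the other lesions.

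A reader might also infer that the Week 4 start of the sensitivity window lets rescued subjects into the main rate. It does not. The window belongs to the sensitivity analysis, and protocol-allowed rescue begins at Week 8, so only off-protocol rescue before Week 4 is missed.

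Finally, testing of secondary endpoints is exploratory, and the rescue-as-failure result will be produced anyway. Both points lower the stakes. Neither tells the reader which rate is the main one.

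**Conclusion.** The conflict is real on either reading of the SAP. The protocol makes a rescued subject a HiSCR50 nonresponder among all ITT subjects. The SAP either scores that subject on counts or drops the subject, and does not declare the change.

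The size is modest and rests wholly on assumed response and rescue rates: about 0 to 4 points in the difference, well inside a standard error of about 10.5 points. The 4-point case needs rescued subjects to meet HiSCR50 more often (40%) than unrescued placebo subjects (30%), which is unfavourable given that treated lesions stay in the count.

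It is tempting to conclude that the treatment effect is biased toward zero because placebo subjects are rescued more. The documents do not support a direction. On the literal reading the sign follows whichever arm is rescued more, and equal rescue gives no shift. On the dropped reading it depends on the response rates as well. Nor do the documents single out HiSCR50 as the endpoint that drives development; SAP 3.4 names the primary and secondary endpoints together. The point should be corrected, but it does not threaten the primary analysis.

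**What to change.** In SAP 7.5.2.2, state that in the main HiSCR50 analysis any rescue medication or rescue procedure from first dose to before the Week 16 assessment is nonresponse. Take rescue from both CRF pages in SAP 6.1.3. The present sensitivity wording names only medications and may miss incision and drainage. Put all ITT subjects in the denominator, with missing Week 16 data as nonresponse, as Protocol 9.4.6 and 9.4.6.1 require, and align the ratio in SAP 6.2.3. Make the analysis on observed counts regardless of rescue the sensitivity analysis.

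If the sponsor prefers the SAP's present approach, state in 7.5.2.2 whether post-rescue counts are used or set to missing, and declare and justify the departure in Section 8.

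Dropping the Week 4 lower bound is a minor tidy-up.

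The cost is SAP wording and programming of rules on data already collected. Reported response rates would be somewhat lower.
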